2.4 The secondary endpoints

- 1) progressive lung function impairment between 3 and 12 months, defined as $\geq 10\%$ relative decline in FVC, or $\geq 10\%$ relative decline in DLco, or increasing radiological extent of PC-ILD using image analysis [20].
- 2) Resolution of ILD, as defined by $\geq 10\%$ relative improvement in FVC, DLco, or reduction of radiological extent.

- 3) Persistence of ILD in those not meeting definition of progression or resolution
- 4) Presence of interstitial lung abnormalities (ILA) on radiological images that do not meet definition of ILD.
- 5) A comprehensive series of clinical, molecular, MRI and biochemical parameters will be assessed as biomarkers.

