	Assess impact of COVID19 on aerobic capacity and endurance.	Incremental shuttle walk test or cardiopulmonary exercise test, if clinically indicated	3 month, 6 months (+/- 6 weeks) and 12 months (+/- 3 months) post SARS-CoV-2 infection
Exploratory	Exploratory circulating biomarkers will be correlated with ILA/ILD	whole blood RNA sequencing (including peripheral blood mononuclear cells) and analysis of epigenetic modifications and proteomics	3 month, 6 months (+/- 6 weeks) and 12 months (+/- 3 months) post SARS-CoV-2 infection
	Compare serological and cellular measures of epithelial and endothelial injury and thrombosis	Serum biomarkers of epithelial and endothelial injury, NETosis and thrombosis Cellular measurements in these same patients. Serum/ Plasma: Nordic biomarkers, LRG-1, MMP-7 etc; NETs	3 month, 6 months (+/- 6 weeks) and 12 months (+/- 3 months) post SARS-CoV-2 infection
	Compare genetic risk factors for lung fibrosis and radiological progression, continuously and dichotomised	genome-wide array genotyping Genetic testing from blood/ saliva of putative candidate genes and use of GENOMIC data, and telomere length in a subset	No sooner than 3 month visit
	Assess the relationship between routinely collected laboratory parameters markers	Laboratory parameters (including CRP, FBC) and extent of ILD in patients	3 month, 6 months (+/- 6 weeks) and 12 months (+/- 3 months) post SARS-CoV-2 infection

3.2 Description of study procedure(s) Tier 1 and Tier 2

Initial patient approach

Eligibility assessment by clinical team

Study information and invitation letter provided to eligible patients for data only, Tier 1 participation.

Description of study procedure(s) Tier 2

History and Examination (10 mins) : Medical history, allergies, medications and anthropometric measurements including height, weight, and body mass index will be recorded during the study visit (or taken from the hospital notes. Or PHOPS data)

Blood sample collection (10 mins) :

Samples will be taken for plasma/ serum for epithelial and endothelial damage biomarkers, coagulation and genetics

Questionnaires (45 mins)

Participants will be provided with seven questionnaires; 36 Short-Form Survey (SF-36), Clinical Frailty Scale (CFS), Patient Health Questionnaire 9 (PHQ9), Montreal Cognition Assessment (MOCA), Dyspnoea-12 score, EQ5D-5L, FACIT-F at the end of each study visit.

There are no investigations required for participants co-enrolled in the PHOSP-COVID study.

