6.4 Serious AEs

An SAE form should be completed and emailed to the Chief Investigator within 24 hours. However, relapse and death due to COVID -19, and hospitalisations for elective treatment of a pre-existing condition do not need reporting as SAEs.

All SAEs should be reported to the London Riverside REC where in the opinion of the Chief Investigator, the event was:

- 'related', ie resulted from the administration of any of the research procedures; and
- 'unexpected', ie an event that is not listed in the protocol as an expected occurrence

Reports of related and unexpected SAEs should be submitted within 15 days of the Chief Investigator becoming aware of the event, using the NRES SAE form for non-IMP studies. The Chief Investigator must also notify the Sponsor of all related and unexpected SAEs.

Local investigators should report any SAEs as required by their Local Research Ethics Committee, Sponsor and/or Research & Development Office.

Contact details for reporting [contact]**CI email (and contact details below)****Fax: N/A, attention [name]****Please send SAE forms to: [contact]****[contact] (Mon to Fri 09.00 – 17.00)****7.0 STATISTICS AND DATA ANALYSIS**

The prevalence of MDT-confirmed PC-ILD at both early (up to 6 months) and again at late (10-15 month) time-points and will be assessed within the total study population. The prevalence of broader radiological abnormalities and phenotypic patterns will also be assessed in a descriptive analysis, together with demographics, haematological and biochemical profiles, physiological performance, and patient-reported outcome measures. Analyses will be performed overall and stratified according to hospitalised and non-hospitalised, as well as severity of infection in hospitalised patients defined above.

Baseline and longitudinal changes in biomarkers reflecting PC-ILD evolution, including circulating factors and cell-types from detailed serological and cellular analysis, will be assessed in multilevel models for repeated measures to test associations according to the presence or absence of PC-ILD at late time points (10-15 months), and according to progression, resolution, or persistence of radiological patterns over follow up time points.

Analyses will be performed using standard epidemiological and statistical genetics methodology. This will include cross-sectional and longitudinal studies, and analyses of disease prevalence and incidence.

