Analysis design and choice of controls will be dependent upon the precise nature of the research question. Identification of risk factors for a specific COVID-19 sequela would involve controls both from within UKILD-Long COVID (without the sequela) and serology-positive controls with prospective questionnaire and healthcare record linkage from Longitudinal Population Studies (for example, UK Biobank, Coronagenes, EXCEED) and pre-existing disease cohorts. Analyses aiming to characterise and understand the clinical features, subtypes and trajectories of sequelae (for example, sarcopaenia) would evaluate the cross-sectional and longitudinal clinical data and biomarkers of UKILD-Long COVID participants who are presenting with the sequelae being studied.

The participant organisations making up the UKILD-long COVID study group have extensive experience of development of, and collaborative use of, disease-specific and general population cohort studies both nationally and internationally enabling access to control populations and alignment of research strategies for rapid validation and replication of findings.

Statistical significance thresholds will be defined in advance of each analysis and will take into account issues of multiple testing and *a priori* evidence.

Data and all appropriate documentation will be stored for a minimum of 10 years after the completion of the study, including the follow-up period.

Project statistician: [name] email:

[contact]
National Heart and Lung Institute
[name]
[name]

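### The section 7.0 biomarker models have no level for interstitial lung abnormalities (ILA), so ILA-only participants fall by default into the PC-ILD-absent group and the ILA part of the table 3.1 aim gets no estimate

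*Combined protocol and SAP*

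**What the plan says.** Section 2.4, item 4, makes ILA an endpoint separate from ILD: "Presence of interstitial lung abnormalities (ILA) on radiological images that do not meet definition of ILD". Table 3.1 also lists persistence of ILAs at 12 months, with the outcome-measure cell left empty.

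In the exploratory part of table 3.1, one row reads "Exploratory circulating biomarkers will be correlated with ILA/ILD". The table does not say whether the slash means the two findings pooled or each in turn.

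Section 7.0 plans multilevel repeated-measures models for biomarkers, "including circulating factors and cell-types from detailed serological and cellular analysis". They are to "test associations according to the presence or absence of PC-ILD at late time points (10-15 months"), and also "according to progression, resolution, or persistence of radiological patterns over follow up time points". ILA is not named in either contrast. For its prevalence analysis, section 7.0 counts PC-ILD as confirmed by the MDT.

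For risk factors, section 7.0 takes internal controls from participants who lack the sequela under study and adds external serology-positive controls. It gives no rule for ILA.

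**The concern.** A participant with ILA only does not have ILD by the plan's own definition. A two-level split on late PC-ILD therefore leaves that person on the absent side, mixed with people whose scans are clear. This has two consequences.

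- The model has no ILA term, so the only biomarker model in the plan cannot deliver the ILA half of the table 3.1 aim.
- If ILA carries part of the biomarker change seen in ILD, the reference mean moves toward the ILD mean and the estimated difference shrinks.

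An analyst who instead follows table 3.1 and pools ILA with ILD moves the same people to the other side and estimates something else. Section 7.0 promises advance definition for significance thresholds only, so the choice could be made after the data are seen. Biomarkers are also secondary endpoint 5 in section 2.4, and risk factors belong to the first secondary objective in 2.2, so the effect is not confined to one exploratory row.

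**Working it through.** The plan gives no sample size, effect size, ILA prevalence or ILA biomarker level for these analyses, so it has no figure to reproduce. What follows is an illustration on stated assumptions.

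**Inputs (all assumed).** p = share with PC-ILD at the late read = 0.15. q = share with ILA only = 0.10 to 0.30. k = mean biomarker shift in ILA as a fraction of the ILD shift = 0 to 0.75. The clear-scan mean is set to 0, the ILD mean to 1, and the variance is equal across groups.

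**Formulas.**
- 7.0 split (ILA in the reference group): the reference mean is qk/(1 - p), so the contrast is 1 - qk/(1 - p).
- Pooled reading of 3.1 (ILA with ILD): the contrast is (p + qk)/(p + q).
- ILD versus clear, with ILA held apart: the contrast is 1 for every k.

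**Central case, q = 0.20 and k = 0.5.** 7.0 split: 1 - 0.10/0.85 = 0.882. Pooled: 0.25/0.35 = 0.714.

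**Share of the ILD-versus-clear difference shown (7.0 split / pooled), p = 0.15:**

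| q | k = 0 | k = 0.25 | k = 0.5 | k = 0.75 |
|---|---|---|---|---|
| 0.10 | 1.00 / 0.60 | 0.97 / 0.70 | 0.94 / 0.80 | 0.91 / 0.90 |
| 0.20 | 1.00 / 0.43 | 0.94 / 0.57 | 0.88 / 0.71 | 0.82 / 0.86 |
| 0.30 | 1.00 / 0.33 | 0.91 / 0.50 | 0.82 / 0.67 | 0.74 / 0.83 |

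The 7.0 split runs from 0.74 to 1.00. The two codings agree when k = (1 - p)/(1 + q), which is 0.77, 0.71 and 0.65 for q = 0.10, 0.20 and 0.30. Below that value pooling loses more; above it the 7.0 split loses more.

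**Sensitivity to p.** Section 1.1 cites up to 24% with fibrotic change on the initial CT. Used only as a scale, p = 0.24 with q = 0.20 and k = 0.5 gives 0.87 for the 7.0 split and 0.77 for pooling. At q = 0.30 and k = 0.75 the 7.0 split falls to 0.70.

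**Information for a test, per participant (p = 0.15, q = 0.20).**
- PC-ILD versus none: p(1 - p - q)/(1 - q) = 0.15 × 0.65/0.80 = 0.122, whatever the value of k.
- 7.0 split: p(1 - p) × contrast² = 0.1275 × contrast². At k = 0.5 this is 0.1275 × 0.882² = 0.0993. At k = 0 it is 0.1275.
- The 7.0 split therefore has 0.0993/0.1219 = 81% of the information of PC-ILD versus none at k = 0.5. At k = 0 the order reverses, and PC-ILD versus none has 0.1219/0.1275 = 96%, a loss of about 4%.
- Ordered scores 0, 0.5, 1: the score variance is 0.20 - 0.25² = 0.1375. At k = 0.5 the 7.0 split has 0.0993/0.1375 = 72% of the trend test's information, but those scores match the assumed truth exactly. At k = 0 the trend test has (0.15 - 0.25 × 0.15)²/0.1375 = 0.092, which is 72% of 0.1275. The trend therefore suits a secondary test.

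**The case against.** A reader might infer that table 3.1 pools ILA with ILD, that 7.0 deliberately keeps ILA in the comparator, that the same biomarker must therefore give two answers, and that 7.0 is the section that dilutes. The documents do not support that. The slash is undefined. The place of ILA-only participants in 7.0 follows from a definition, not from a stated rule. The 3.1 row lists RNA sequencing, epigenetic and proteomic assays, and the circulating factors in 7.0 may overlap with these without being shown to be the same. Dilution in 7.0 needs k above 0, and in most of the table above pooling loses more.

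The plan is also not silent on flexibility: "Analysis design and choice of controls will be dependent upon the precise nature of the research question". If the sequela studied is ILA and ILD together, controls without it would exclude ILA. Section 1.2 describes a control cohort free of ILD features. Section 7.0 has a second biomarker contrast, on the course of radiological patterns, and describes broader radiological abnormalities. These points soften the case but do not close the gap. The control cohort is set at about 3-6 months, without saying whether an ILA scan disqualifies, whereas the model groups by late status. An open choice of controls is not a rule, and the second contrast does not define the reference group of the first.

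The strongest objection concerns the estimand. ILD against everyone without ILD is a legitimate question, and a prognostic marker may need to separate ILD from ILA as well. Comparing only with clear scans could overstate discrimination. This stands, and it is why the planned contrast should be kept and not replaced.

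**Conclusion.** The point holds in a limited form. Table 3.1 names ILA as a biomarker target, while the 7.0 models have no ILA level and by definition leave ILA-only participants in the reference group. If ILA biomarker levels lie between clear scans and ILD, the 7.0 contrast understates the ILD-versus-clear difference. It shows about 74-100% of it under 15% PC-ILD, 10-30% ILA and an ILA shift of 0-75% of the ILD shift, with no loss at a zero shift. Pooling would show 33-90% over the same range. All of these inputs are assumptions.

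What the documents support is that the two sections can give different answers, not that they must. The primary endpoint, prevalence of ILD, is unaffected. Severity is modest: worth settling before the biomarker analyses, but not a flaw in the main result.

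**What to change.** - In the 7.0 biomarker models, enter late status as a three-level factor (none, ILA, PC-ILD) among participants with a late read.
- Report PC-ILD versus none and ILA versus none alongside the planned PC-ILD versus not-PC-ILD contrast. Add an ordered trend as a secondary test.
- Reword the 3.1 row to match, so that the slash no longer needs interpreting.
- In the 7.0 paragraph on choice of controls, report internal-control risk-factor analyses for ILD with ILA-only participants shown as a separate group.

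**Cost.** The status factor takes one extra degree of freedom, and more if it interacts with time. The none group is smaller than the planned reference group: PC-ILD versus none carries about 4% less information if ILA has no shift, at 15% PC-ILD and 20% ILA. No new endpoint is needed, since ILA is already listed in 2.4 and 3.1. The change is a little more than wording, because the plan gives no reading criterion for ILA and one must be written down. The visit 1 list that is repeated at visit 3 contains no CT, and section 3.3 takes imaging from clinical care. The number with a late read should therefore be reported for each group.

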3.2.1 Baseline and follow up assessments

Initial patient approach

Eligibility assessment by clinical team

Study information and invitation letter provided to eligible patients

Visit 1 (~3 months) (Post COVID-19 infection patients)

1. Review of eligibility with participant
2. Obtain written informed consent
3. History and anthropometric measurements, e.g. height, weight, body mass index (BMI)
4. Blood sample (6-10 ml) collection
5. Pulmonary function test (20 minutes)
6. *Optional* 6-minute walk test (6MWT) (10 minutes)
7. Quality of Life questionnaire (SF-36) (10 minutes)
8. Clinical Frailty Scale (CFS) (5 minutes)
9. Personal health questionnaire (PHQ) (10 minutes)
10. Montreal Cognitive Assessment MOCA (10 minutes)
11. Dyspnea 12 score (10 minutes)
12. EQ5D-5L (10 minutes)
13. FACIT-F questionnaire (10 minutes)

Optional Visit 2 (~6 months) (Post COVID-19 infection patients and matched controls)

All visit 1 assessments will be repeated.

Visit 3 (~12 months) (Post COVID-19 infection patients)

All visit 1 assessments will be repeated.

Visits will be scheduled to take place over 1 day.

Visit 2 is optional,

Visits 1 and 3 are obligatory.

3.3 Monitoring of clinical events and re-analysis of previous scans (clinically indicated)

Clinical outcome data and images from clinical scans for all COVID-19 patients will also be collected from around the time of infection and hospitalisation and follow up. Laboratory analyses and chest imaging results undertaken for clinical reasons will also be collected. Access to participant medical records and any relevant hospital data that is recorded as part of routine standard of care; i.e., CT-Scans, blood results and disease progression data etc. will be obtained with patient consent from hospital electronic patient records and NHS digital

3.4 Sample Handling Tier 2

Blood samples for the analysis of serum inflammatory markers, serum biomarkers of endothelial and epithelial injury and coagulation studies, viral serology, viral PCR, and whole genome sequencing, ribonucleic acid sequencing and flow cytometry in blood will be collected. Analysis of venous blood samples will be performed in local NHS laboratories. If the Participant consents approximately 10 ml of blood will be stored in the Division of Cardiovascular Medicine for further analysis as part of collaborations with other groups. Samples will not be collected from participants who are also participating in PHOSP-COVID

4.0 PARTICIPANT RECRUITMENT

4.1 Pre-recruitment evaluations

Screening and Eligibility Assessment

Patients will be assessed by the clinical teams for eligibility against the inclusion or exclusion criteria for Tier 1 and/or Tier 2.

The clinical teams at the recruiting sites will confirm that patients have been infected with SARS-CoV2 before approaching them. Participants must satisfy all the approved inclusion and exclusion criteria of the protocol. If eligible for Tier 1, a 'data only' participation, once criteria is confirmed consent can be taken by phone. Participants will then be invited to join the study and informed consent will be obtained at the start of visit 1. For Tier 2, pre-screening for eligibility will take place prior to consent. It will be done by the direct care team using patient notes. There will be no access to patient identifiable data outside of the direct care team prior to consent.

Screening and eligibility for PHOSP COVID/C-MORE participants

For PHOSP-COVID participants, screening and eligibility assessment will occur as per the REC approved protocol (IRAS ID 285439).

All patients can be directed to other relevant post-COVID studies, including but not restricted to POSTCODE and XMAS.

4.2 Inclusion Criteria

Tier 1 criteria 'Data Only' participation

- 1) Age >18 years old -99 years old
- 2) Evidence of SARS-CoV-2 infection confirmed by PCR or serology at any point during the duration of the pandemic
- 3) Breathlessness and/or a clinical indication for a chest CT scan as per clinician judgment
- 4) Participants who have been identified and consented for tier 1 may not meet the inclusion criteria for tier 2 (below) but consent to researcher access to all clinical data relating to their health care during the pandemic and any subsequent follow up in relation to their COVID recovery.

Tier 2

- 1) Age >18 years old -99 years old
- 2) Evidence of SARS-CoV-2 infection confirmed by PCR or serology 3 months (+/- 6 weeks) earlier
- 3) Clinical indication for a chest CT scan as per clinician judgment
- 4) Participants who have been identified and consented for the main PHOS-PCOVID study are also eligible to join this study (if PHOSP-COVID is still open to recruit at that time).
- 5) Allow inclusion of patient who are receiving up to 10mg of prednisolone a day

4.3 Exclusion Criteria

- 1) Life-limiting illness within 12 months
- 2) Significant pre-existing lung disease prior to March 2020, which in the investigator's judgement could make the chest CT scans difficult to interpret

4.4 Withdrawal Criteria

Early Discontinuation/Withdrawal of Participants : During the course of the study a participant may choose to withdraw early from the study treatment at any time. This may happen for several reasons, including but not limited to:

- The occurrence of what the participant perceives as an intolerable AE.
- Inability to comply with study procedures
- Participant decision

According to the design of the study, participants may have the following three options for withdrawal;

- 1) Participants may withdraw from active follow-up and further communication but allow the study team to continue to access their medical records and any relevant hospital data that is recorded as part of routine standard of care; i.e., CT-Scans, blood results and disease progression data etc.
- 2) Participants can withdraw from the study but data and samples obtained up until the point of withdrawal to be retained for use in the study analysis. No further data or samples would be collected after withdrawal.

- 3) Participants can withdraw completely from the study and withdraw samples collected up until the point of withdrawal. The samples already collected would not be used in the final study analysis.
- 4) In addition, the Investigator may discontinue a participant from the study at any time if the Investigator considers it necessary for any reason including, but not limited to:
 - Ineligibility (either arising during the study or retrospectively having been overlooked at screening)

Participants that choose to withdraw from the study will not be replaced. The type of withdrawal and reason for withdrawal will be recorded in the CRF. If the participant is withdrawn due to an adverse event, the Investigator will arrange for follow-up visits or telephone calls until the adverse event has resolved or stabilised.

5.0 ASSESMENT AND FOLLOW UP

5.1 Optional follow up and assessment

As previously detailed in section 3.3 above, Tier 2 participants may also agree to a final follow up assessment and an optional interim assessment

Optional Visit 2 (~6 months) (Post COVID-19 infection patients and matched controls)

All visit 1 assessments will be repeated. All visit 1 assessments will be repeated.

Visits will be scheduled to take place over 1 day. Visit 2 is optional, visits 1 and 3 are obligatory. For research specific visits, participants will be offered reimbursement for travel expenses. This includes reimbursement for petrol, car parking, taxis.

Clinical outcome data and images from clinical scans for all COVID-19 patients will also be collected from around the time of infection and hospitalisation and follow up. Laboratory analyses and chest imaging results undertaken for clinical reasons will also be collected. Access to participant medical records and any relevant hospital data that is recorded as part of routine standard of care; i.e., CT-Scans, blood results and disease progression data etc. will be obtained with patient consent from hospital electronic patient records and NHS digital. The end of the study will be the point at which the final patient follow-up and assessment have been completed.

A detailed Image Management protocol for the UKILD-Post COVID Study provides a comprehensive outline of the purpose, operation, methods, policies, and governance of Image collection for UKILD. It describes the procedures used to collect and store images. (appendix 1)

